10.1 Blood glucose < 70 mg/dL (Hypoglycemia)

- For the purposes of this study, hypoglycemia will only be addressed as an adverse event for clients who have a screening blood glucose result < 70 mg/dL, **and** who report a history of diabetes
 - Some clients with a diabetes history (especially if their diabetes is poorly controlled) may report hypoglycemic symptoms at a higher threshold (e.g., < 100 mg/dL); in these cases it is appropriate to treat the symptomatic client as if hypoglycemic and document as an adverse event
 - While some conditions exist that may cause hypoglycemia in people without diabetes, these conditions are extremely rare
 - For clients who do **not** report a history of diabetes and have a screening blood glucose < 70mg/dL, it is not necessary for study staff to treat or report as an adverse event
- In clients reporting a diabetes history, any blood glucose lower than 70 mg/dL is considered low (“hypoglycemia”) and requires immediate intervention to bring the glucose level up into a normal range.
- The GE100 Blood Glucose Monitor displays results between 20 and 600 mg/dL (if a test result is under 20 mg/dL, the meter will display “Lo” – in this event repeat test to confirm correct glucose level).
- A client / study participant with a blood glucose < 70 mg/dL should immediately be given an appropriate hypoglycemia snack (15 grams of quickly absorbing carbohydrate). Study staff should stock pre-packaged glucose tabs (e.g., “Dex4 Glucose Tablets”) during all blood testing and DSME events to use in these cases (note: 1 Dex4 glucose tab contains approximately 4 grams of CHO; clients experiencing hypoglycemia should thus receive 4 tablets).
- Study staff should recheck the client’s blood glucose 15 minutes after the client consumed the snack. If the client’s blood glucose level has not increased to over 70 mg/dL, repeat dosing of glucose tablets / hypoglycemic snack and recheck glucose levels every 15 minutes until the glucose returns to a normal level.
- Caution client against eating / drinking too much fast-acting carbohydrate too quickly (e.g., more than 15 grams every 15 minutes) in order to prevent post-treatment hyperglycemia.
- Once the client is experiencing normoglycemia, a longer-acting complex carbohydrate snack (peanut butter and crackers, cheese and crackers, nut and raisin mix, yogurt and fruit, half a whole grain bagel with cream cheese, etc.) should be given to help maintain normal blood glucose levels if the next planned meal or snack is more than 1-2 hours away.
- Effort should also be made to identify the underlying cause of the hypoglycemia in order to help avoid future episodes.
- Refer client as needed to PCP or local community health center for further evaluation and treatment management.
- These events should be reported in the MS Access database for all study participants.

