3.1.1 Testing for diabetes and diabetes control among food pantry clients

In order to identify food bank clients who may be eligible for study participation, food bank project staff will offer free diabetes screening events at food pantry sites during the recruitment phase of the study. Diabetes screening will be provided at no cost for any food pantry client who is interested in and verbally consents to the screening, and is over 18 years of age. Food bank staff will conduct all screening activities, emphasizing with food pantry clients that screening tests are **not** diagnostic and that clients should speak directly with their health care providers for diabetes risk assessment, evaluation, and treatment.

For food pantry clients with no reported history of diabetes, or no known history of diabetes, diabetes screening will first include a random blood glucose (RBG) test using a Point-of-Care (POC) glucometer and a finger stick capillary whole blood sample. Clients who have an elevated RBG screening result (defined as ≥ 160 mg/dL in non-fasting individuals and ≥ 140 mg/dL in fasting individuals) will also receive a screening glycosylated hemoglobin A1C (HbA1c) test using a POC device.

All screening tests will be performed by trained study or food bank staff, or by trained food bank volunteers. All study staff and volunteers with human subjects contact must have appropriate CITI certification and quality and safety training. Screening staff will complete the information on the Screening Log (Appendix B) for **every** food pantry client who receives a blood glucose and/or HbA1c test. If uncertain, staff can ask the client for specific information in order mark the appropriate boxes under “age”, “gender”, and “race/ethnicity” (otherwise, staff can complete that information based on their assessment of the client.

For food pantry clients who self-report a history of diabetes, screening will consist of a POC HbA1c test using a finger stick capillary whole blood sample performed by trained personnel.

All clients who participate in screening will receive written results of their screening tests (see Client Screening Results Form in **Appendix J**), along with basic information about their results and local community health care resources.

Additionally, any food pantry client who receives an HbA1c test will receive an educational handout (see **Appendix AK**) with information about the category in which their result falls:

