3.1.3 Testing Glycosylated Hemoglobin (HbA1c) Levels

We will measure HbA1c levels for food pantry clients who report a diabetes history or who have a screening RBG result ≥ 160 mg/dL non-fasting or ≥ 140 mg/dL fasting. We will use a point-of-care (POC) HbA1C device using a small sample (1 large drop, 5 microliters [μ L]) of capillary whole blood. Instructions for using the PTS Diagnostics HbA1c+NOW[®]™ system can be found in **section 7.3**.

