3.1.4 Monitoring blood glucose control among study participants

Our primary outcome of interest is change in HbA1c over time for study participants. Hemoglobin A1c testing provides a reliable estimate of general blood glucose control over an approximate three-month time frame. We include regularly scheduled HbA1c testing for all study participants throughout the course of the study following the timeframes outlined below. All HbA1c testing will be conducted by trained food bank staff or volunteers, who will use the same POC HbA1c devices described above (and in specific detail in **section 7.3**). We will conduct monitoring tests with study participants at the food pantries where participants will be going to receive food bank services. Study staff can use the “Participant Follow-Up Testing Results” form (**Appendix AU**) to record all follow-up and monitoring participant test results. All test results will be entered into the MS Access database; the database has fields for recording test results performed outside of the windows identified below.

	Intervention Group	Control Group
T0 (baseline)	At enrollment	At enrollment
T3 (month 3)	2 – 4 months (3 \pm 1)	N/A
T6 (month 6)	5 – 7 months (6 \pm 1)	5 – 7 months (6 \pm 1)
T9 (month 9)	N/A	8 – 10 months (9 \pm 1)
T12 (month 12)	11 – 13 months (12 \pm 1)**	11 – 13 months (12 \pm 1)**

* 1 month = 30 DAYS ALWAYS

** Alternatively, T12 HbA1c windows can be manually calculated as 5-7 months **after** the completion date of a participant’s T6 follow-up activities. This revision will accommodate participants who complete their T6 activities at month 5 (earliest part of the window) and maintain a 5-7 month separation between the T6 and T12 follow-up activities.

Study staff can complete “extra” HbA1c testing for study participants outside of their intervention windows (e.g., between T0 and T6 for CONT group, or between T6 and T12 for INT group) **if** a participant requests a test during a pantry visit. Staff should not complete more than 1 extra HbA1c test for a participant during their waiting period. Staff should not promote extra HbA1c testing for study participants—the primary purpose for completing extra testing during these periods is to provide a positive experience for study participants. Extra HbA1c test results should be entered in the Access database in one of the “extra test” fields.

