9.4 Final Study/Early Discontinuation Evaluations

Participants should be actively followed through all study visits till the final visit, unless he or she withdraws informed consent.

It is important to note that if a study participant discontinues any part of the intervention but does NOT actively withdraw informed consent, he/she should still be followed to the end of the study. That is, participants in any component of the intervention (e.g. picking up food boxes, attending educational sessions) should still have HbA1c testing and complete follow-up survey as regularly scheduled.

10 Adverse Events and Safety Reporting

All adverse events should be reported to UCSF and [name] (FANO) **within 24 hours**. Study staff should complete an “Adverse Event” report (**Appendix AN**) for each incident that occurs, and enter the data into the MS Access database (if appropriate [involves a study participant] and when possible).

An adverse event can include study participants, or include study staff and food pantry clients that participate in any study activity (e.g. blood glucose screening event). An adverse event report should be completed for all events, with the one exception of low blood glucose screening results for pantry clients who do not report a history of diabetes. Food pantry clients with a blood glucose screening result < 70 mg/dL who do not report a history of diabetes do not require treatment by study staff, and the event does not need to be reported as an adverse event.

Adverse events which are reasonable to anticipate include:

1. Low blood glucose (hypoglycemia)
2. High blood glucose (hyperglycemia)
3. Reports of suicidality or homicidality
4. Reports of elder abuse or neglect
5. Reports of poor food quality
6. Study related injury

Each of these adverse events, along with steps on how to address, are discussed below.

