Appendix AN – Adverse Event Reporting Form

ADVERSE EVENT REPORTING FORM

Date: _____

Site: ACCFB GCFB HFB

Pantry Site / Location:

Person completing form:

List of people involved in incident:

If incident involves a pantry client, does the client report a history of diabetes? Yes No

If incident involves a pantry client, is the client a participant in the study? Yes No

If “Yes”, Participant ID#: _____

Adverse Event:

- Low blood glucose (hypoglycemia: report and treat clients reporting a diabetes history)
- High blood glucose (hyperglycemia: report only when action is required for symptomatic clients)
- Reports of suicidality or homicidality
- Reports of elder abuse or neglect
- Reports of poor food quality
- Study related injury
- Other:

Description of Incident:

Action Taken:

Follow-up Action Required:

Date Reported to Study Coordinating Center ([name], FANO): _____

Date Entered in MS Access (if event involved study participant): _____

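### Section 10.1 ties the hypoglycemia adverse event to a screening glucose that clients reporting diabetes do not routinely receive, and it conflicts with section 10 and Appendix AN

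*Combined protocol and SAP*

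**What the plan says.** **Reporting rule.** The first bullet of section 10.1 says that "hypoglycemia will only be addressed as an adverse event for clients who have a screening blood glucose result < 70 mg/dL", and adds a second condition: they must be clients "who report a history of diabetes". Later text in 10.1 is wider. It treats any value under the same cut-off in a client reporting diabetes as low and needing action. A sub-bullet has symptomatic clients with a diabetes history documented as adverse events at a higher value. The section ends by asking for database entry for all study participants.

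Section 10 sets a general rule that every event gets a report, with a single exception: "Food pantry clients with a blood glucose screening result < 70 mg/dL who do not report a history of diabetes do not require treatment", and such results need not be reported. The tick box in Appendix AN begins "Low blood glucose (hypoglycemia: report and treat clients reporting a diabetes history" and has no screening condition.

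**Who is glucose-tested.** Under section 3.1.1, for clients "with no reported history of diabetes, or no known history of diabetes, diabetes screening will first include a random blood glucose (RBG) test". By contrast, "For food pantry clients who self-report a history of diabetes, screening will consist of a POC HbA1c test". Section 3.1.3 agrees: "We will measure HbA1c levels for food pantry clients who report a diabetes history". After enrollment, section 3.1.4 says "We include regularly scheduled HbA1c testing for all study participants throughout the course of the study", and its table contains no glucose test.

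Other places point the other way. Section 7.2 foresees glucometer use in study participants. Section 10.2 gives steps for a participant's glucose result. Appendix E lists both glucose and HbA1c for the control arm at T0. Appendix AI records a glucose result alongside diabetes history, Appendix AU has a glucose field for follow-up, and Appendix AZ tells providers that glucose and HbA1c are checked four times in 12 months.

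**Other capture of hypoglycemia.** Section 13.4.3 lists self-reported severe hypoglycemic events as a secondary outcome. Section 13.5.1 collects diagnosis codes from providers, and section 13.5.2 plans to look at them with severe hypoglycemia in mind.

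**The concern.** The group that is routinely given a screening glucose is the group whose low results are exempt from reporting. The group whose low results are reportable is routed to HbA1c instead. Every enrolled participant has HbA1c of at least 7.5% (section 5.2), the intervention changes food supply and self-management, and low blood glucose comes first in section 10's list of events to anticipate.

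Reports are foreseeable. Section 3.4.2 has staff ask participants at food pick-ups about difficulties with their diabetes. If someone describes a low at home, the lead rule in 10.1 generates no report. Section 16 plans no data and safety monitoring board, and the six-monthly internal review excludes analysis of study data. A short list of hypoglycemia events at the end of the trial could be taken as reassurance when it partly reflects what the rule allowed staff to record.

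**Working it through.** No arithmetic applies beyond comparing thresholds. The check sets the rules side by side.

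**Step 1: can the lead rule be met at screening?** It needs a screening glucose below 70 mg/dL and a reported diabetes history.
- History reported: 3.1.1 and 3.1.3 specify HbA1c and name no glucose test, so the first condition has no routine route.
- No history reported: glucose is tested, but the second condition fails, and sections 10 and 10.1 exempt the result.
- No history reported, then enrolled: HbA1c follows only if glucose is at least 140 mg/dL fasting or 160 mg/dL non-fasting. Both exceed 70, so the glucose result that led to enrollment cannot have been low.

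**Step 2: can it be met after enrollment?** The tables in 3.1.4, the visit list in 9.1 and Appendix E schedule only HbA1c at T3, T6, T9 and T12. If staff do take a glucose, as Appendix AU allows, it is a follow-up result and not a screening one on the wording of 10.1.

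**Step 3: what does each text say about the same case?**

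| Case | 10.1, first bullet | Section 10 | Appendix AN |
|---|---|---|---|
| No history, low screening glucose | Not an event | Exempt | Outside the box's wording |
| History reported, low screening glucose | Event, but no routine test | Report | Report |
| Enrolled, low glucose at follow-up | Not an event | Report (outside the exception) | Report |
| Enrolled, past episode at home, told to staff or in a survey | Not an event | Not addressed specifically | Not addressed |

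The third row is a direct contradiction. The fourth is a gap. The symptomatic sub-bullet of 10.1 softens the third row for a client with symptoms, but it reads as a current event in front of staff and does not deal with a past episode.

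**Step 4: does the plan handle reported events elsewhere?** Yes. Under 10.5, a participant's report of illness from program food requires the adverse-event form. Under 10.6.4, so does a reported infection from screening. Hypoglycemia has no matching rule.

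**Step 5: is opportunity to report equal between arms?** No. Section 9.1 lists 11 food pick-ups for the intervention arm from T0 to T6, plus classes and a T3 test. Waiting controls have ordinary pantry attendance over that period, with the retention contacts of section 4.1 available to both arms. Spontaneous reports would therefore be expected to differ by arm even with equal risk.

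**The case against.** A reader might infer something stronger: that people reporting diabetes are never glucose-tested, that hypoglycemia is excluded by definition, that the recorded count must be zero, and that nothing else would reveal a problem. The documents do not support this, for four reasons.

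- **Testing.** Section 3.1.1 describes routine screening and does not forbid a glucose test. Sections 7.2 and 10.2 and Appendices E, AI, AU and AZ foresee or describe glucose tests in participants or people with diabetes. The screening flow chart announced in section 5.1 is not shown, so the full pathway cannot be seen.
- **Reportability.** Section 10's general rule, the symptomatic sub-bullet and closing instruction of 10.1, and Appendix AN all keep some events reportable. The rules are inconsistent; they do not amount to an exclusion.
- **Other sources.** Severe events are a secondary outcome analyzed by arm under section 13.4.4. Provider diagnosis codes are a second source, and sections 7.7.3 and 7.7.4 seek them even for participants lost to follow-up unless consent was revoked.
- **Ranking of the harm.** Section 10 lists low blood glucose first but does not call it the main harm, and section 1.1 reports a pilot trend toward fewer severe episodes.

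All of this stands against the stronger reading. It does not remove the conflict. Staff cannot follow both the restriction in 10.1 and the general rule in section 10, and mentions of glucose testing elsewhere do not turn a follow-up reading into a screening one. The other sources also have limits. The survey is retrospective and reaches only those who answer. Provider records are incomplete and not timely, with coverage goals of 80% in the intervention arm and 70% in the control arm (section 13.5.3), a gap of 80 − 70 = 10 percentage points. Neither source has a stated link to the 24-hour report.

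**Conclusion.** The concern holds as an inconsistency with a consequence for the safety record. On the literal wording of 3.1.1, 3.1.3, 3.1.4 and 10.1, the lead hypoglycemia rule has almost no routine route to be met in enrolled participants. It contradicts section 10, wider text in 10.1 and Appendix AN, and no rule covers follow-up readings or participant-reported episodes explicitly.

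The rule bears on all 720 planned participants. The number of events that would go unrecorded cannot be estimated, because the documents give no event rate and do not settle how often participants are glucose-tested. If staff follow section 10 and Appendix AN, the loss may be small for lows measured on site. If they follow the first bullet of 10.1, those events would largely be missed as well. Either way, a sparse adverse-event list should not by itself be read as evidence of safety.

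**What to change.** Reconcile sections 3.1.1, 3.1.3, 3.1.4, 10 and 10.1 with Appendices AN and AZ, so that one statement says whether participants are glucose-tested and one reporting rule applies. For enrolled participants, that rule should not depend on a screening test they do not routinely receive. State explicitly whether a low measured at follow-up, and an episode a participant reports at a pick-up, class, call or survey, is entered on the Appendix AN form, and record study arm with it.

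For the between-arm comparison of harm, use the already planned T6 survey outcome, because staff contact differs by arm before T6. Confirm that the item is worded the same in both T6 surveys, which are not shown. List spontaneous reports separately, with a note on unequal contact.

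Glucose thresholds and treatment steps are for the sponsor to reconcile; none is proposed here. The cost is a wording change and some additional adverse-event forms. No new test or visit is needed.

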10.2 Blood glucose > 240 mg/dL, or HbA1c > 9% (Hyperglycemia)

- The GE100 Blood Glucose Monitor displays results between 20 and 600 mg/dL (if a test result is over 600 mg/dL, the meter will display “Hi” – in this event, repeat test to confirm glucose level; perform QC check on meter as necessary).
- The A1C+Now system displays test results up to 12.9% (for results greater than 12.9%, the device will display > 13%).
- If a participant (or client not yet enrolled in the study) has a blood glucose result between 240 – 399 mg/dL, or a HbA1c result between 9% - 12.9%, study staff should refer the client back to their primary care provider for evaluation. If the client or participant does not have a primary care provider, study staff should make a new patient referral to a partner clinic following study protocols. Partner clinic agreements contain recommended timeframes for contacting referred patients with these results (within 1 week) to schedule a patient appointment to occur within 1 month from receiving the referral.
 - Hyperglycemia in the absence of symptoms does not require action by study staff or reporting as an adverse event; all testing results should be recorded and saved in the MS Access database.
- If a participant (or client not yet enrolled in the study) has a blood sugar greater than 400 mg/dL (or confirmed “Hi” reading on the glucometer), or a HbA1c result > 13%, study staff should refer the client back to their primary care provider and/or facilitate an appointment being made. If the client or participant does not have a primary care provider, study staff should make a new patient referral to a partner clinic following study protocols.
 - Food bank – clinic partnership agreements outline that clinics will attempt to contact referred clients with these results within 24 hours, and will schedule appointments for clients experiencing severe hyperglycemia within 72 hours of receiving a referral from the food bank.
 - All clients with severely elevated blood glucose results should also be encouraged by study staff to initiate contact with their PCP or nearest community clinic.
 - Hyperglycemia in the absence of symptoms of study staff action does not require reporting as an adverse event; all testing results should be recorded and saved in the MS Access database.
- If necessary, clients can also be provided with information about local emergency medical care (local Emergency Rooms and hospitals) if the client prefers or needs immediate medical attention.
- If necessary and/or at the client’s request, study staff can also call “911” to initiate the local emergency response system (EMS) to have the client evaluated by health care professionals onsite. Severe hyperglycemia accompanied by any of the following symptoms potentially constitutes a medical emergency and warrants activation of the EMS: nausea and/or vomiting, chest pain, abdominal pain, or altered mental status.
- Only hyperglycemia events where clients report symptoms and study staff respond/act (e.g. activating local EMS) are required to be reported as an adverse event.
 - Complete an Adverse Event Report and contact [name] within 24 hours of event.
 - These events should be reported in the MS Access database for all study participants.

